3.4.2 Protocol Deviations

A protocol deviation is defined as any departure from the approved protocol, including but not limited to deviations related to eligibility criteria, study treatment administration, study assessments, or visit scheduling.

Protocol deviations will be prospectively classified as major or minor prior to database lock and prior to unblinding of biomarker results.

Major Protocol Deviations

Major protocol deviations are defined as deviations that may affect participant safety, the scientific integrity of the study, or the interpretability of the primary endpoint.

Predefined major protocol deviations include:

- Failure to meet inclusion or exclusion criteria with enrolment into the study
- Receipt of incorrect study treatment or dose not consistent with protocol-defined escalation rules
- Discontinuation of study treatment prior to completion of the dose-escalation phase without post-baseline biomarker data
- Use of prohibited concomitant medication with potential impact on safety or pharmacodynamic outcomes
- Missing all post-baseline exosome biomarker assessments

Participants with major protocol deviations may be excluded from specific analysis populations as defined in Section 4.

Minor Protocol Deviations

Minor protocol deviations include deviations that are not expected to materially affect safety or interpretation of study outcomes, such as:

- Study visits conducted outside the protocol-defined visit window
- Isolated missed or delayed assessments
- Administrative or documentation errors

Summary of Protocol Deviations

Protocol deviations will be summarized descriptively by treatment group and overall. The following summaries will be provided:

- Number and percentage of participants with at least one protocol deviation
- Number and percentage of participants with at least one major protocol deviation
- Number and percentage of participants with at least one minor protocol deviation

- Listing of protocol deviations by category and type

Percentages will be calculated using the randomized population as the denominator. No formal statistical testing will be undertaken.

4 Analysis Populations

4.1 Enrolled Population

All participants who sign informed consent.

4.2 Safety Analysis Set (SAF)

All participants who receive ≥ 1 dose of study medication.

4.3 Modified Intent-to-Treat (mITT) Population

All participants who:

- Receive ≥ 1 dose of study medication, and
- Have ≥ 1 post-baseline exosome biomarker assessment

This population is the **primary analysis population** for PD and biomarker endpoints.

4.4 Pharmacokinetic Population

All participants with sufficient PK samples to estimate at least one PK parameter.

4.5 Overview of Outcomes

An overview of the primary, secondary, and exploratory outcomes included in the PATH-1 study is provided in Table 4.4-1. Outcomes are categorized by level, timeframe, and data type to clarify their role in the statistical analyses.

Overview of Study Outcomes

Level	Outcome	Timeframe	Outcome Type
Primary	Change from baseline in exosome biomarkers of pre-programmed cell death, synaptic integrity, neuroinflammation, and AD-related protein trafficking	Baseline to Week 8	Continuous
Secondary (Key)	Safety and tolerability (AEs, SAEs, labs, ECGs, vital signs)	Throughout study	Categorical / Continuous
Secondary	Steady-state pharmacokinetic parameters (e.g. plasma concentrations)	Weeks 2–8	Continuous
	Proportion achieving target AChE inhibition (~45%)	During treatment	Dichotomous
	Time to achievement of target AChE inhibition	During treatment	Time-to-event
	Duration of maintenance of target AChE inhibition	During treatment	Continuous

	Treatment compliance (capsule count, diary)	During treatment	Continuous / Categorical
Exploratory	Change in CSF biomarkers (A β 1-40, A β 1-42, Tau, p-tau)	Baseline to Week 8	Continuous
	Change in plasma biomarkers (p-tau217, NfL)	Baseline to Week 8	Continuous
	Change in FLAME cognitive domain scores	Baseline to Week 8	Continuous
	Change in MoCA total score	Baseline to Week 8	Continuous

5 General Statistical Principles

- All analyses will be conducted using R (version ≥ 4.2) or SAS (version ≥ 9.4)
- Continuous variables: mean, SD, median, IQR, min, max
- Categorical variables: counts and percentages
- No formal hypothesis testing or multiplicity correction
- Emphasis on effect size estimation, confidence intervals, and visualizations
- Outliers and extreme values in biomarker measurements will be retained in primary analyses unless determined to result from assay or data collection errors. Sensitivity analyses may exclude extreme values (e.g., >10 MAD from median) to assess their influence on results. If performed, such analyses will be justified and documented.
- No formal subgroup analyses are pre-planned. Exploratory descriptive summaries may examine biomarker responses by baseline disease severity (early vs. mild AD) or by achievement of target AChE inhibition, but these will be clearly labeled as descriptive and post-hoc.

6 Handling of Missing Data

- No imputation will be performed for missing biomarker or cognitive data
- Analyses will use observed data only in a complete-case manner
- Missingness patterns will be summarized descriptively
- Early termination participants will be included where data are available

Given the short duration and intensive follow-up, missingness is expected to be limited.

7 Primary Endpoint Analysis

Exosome Biomarkers

7.1 Data Structure

For each biomarker panel:

- Pre-programmed cell death
- Synaptic integrity

- Neuroinflammation
- AD-related trafficking

Measurements will be summarized at:

- Baseline
- Week 2
- Week 4
- Week 6
- Week 8

7.2 Statistical Methods

- Change from baseline will be calculated for each time point
- Within-arm trajectories will be visualized using spaghetti plots
- Between-arm comparisons will use:
 - Mean change differences with 95% CI
 - Mixed-effects models will be fitted exploratorily to estimate treatment effects over time.
 - Model specification:
 - Response: Change from baseline in biomarker level;
 - Fixed effects: Treatment (phenserine vs donepezil), Visit (categorical: Weeks 2, 4, 6, 8), Treatment × Visit interaction.
 - Random effects: Random intercept per participant.
 - Covariance structure: Unstructured (if convergence permits, otherwise compound symmetry).
 - Given the small sample size, models may have convergence issues or unstable variance estimates. If models fail to converge, results will be presented descriptively.

8 Secondary Analyses

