10.3. Statistical Analyses

All primary, secondary and exploratory outcomes will be collected for all participants, except that PK analyses will be performed only for participants randomized to phenserine.

Trial management and data management will be conducted by the University Hospital Stavanger Clinical Trials Unit and the trial statistics will be led by [name], King's College London.

Standard safety data (including all AEs, TEAEs, SAEs, important clinical laboratory findings, and AE-related discontinuations) will be summarized for each treatment arm and dose level.

Exosome biomarker values will be natural log transformed to avoid skewness. To assess the effect of phenserine on a given biomarker, a linear mixed-effects model will be used, with treatment groups (phenserine vs donepezil), time, baseline biomarker, and plate to plate variability in exosome concentration (determined by NanoSight) as fixed effects and participant identification treated as a random effect.

To demonstrate that dropout rates are Missing at Random (MAR), we will calculate the correlation between dropout indicators (e.g., whether a participant drops out) and key covariates, including treatment group, baseline characteristics, and other relevant random effect categories. Based on prior observations (liraglutide trial for example), we expect that the likelihood of dropout will largely be explained by observed factors, especially drug treatment status. A logistic regression model will be used, with the dropout indicator as the dependent variable and treatment status, baseline covariates, and any other relevant factors as independent variables. If the model explains a significant portion of the dropout pattern, this would support the MAR assumption. Sensitivity analyses will also be conducted to assess the robustness of this finding under alternative missingness mechanisms.

For clinical secondary and exploratory outcomes, change from baseline will be calculated at the final study assessment (mean, n, standard deviation, standard error, minimum and maximum scores).

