The primary outcome is the difference between treatment groups in key proteins measured in neuronally derived exosomes. Based on the previous work of Goetzl et al(30,31) between group differences of 4.9 SD were achieved in these measures. Assuming a difference of half of this magnitude (2.45 sd), a sample size of 4 participants per arm would be needed to give 80% power to detect a difference between groups to the 0.05 level of significance. The additional participants receiving phenserine will provide valuable information for safety reporting.

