10.3.1. General Considerations

The statistical analysis plan for this study is designed to assess the efficacy, safety, and pharmacokinetic properties of phenserine compared to donepezil in participants with early or mild Alzheimer's Disease (AD). Analyses will be conducted on a modified intent-to-treat (mITT) population, which includes all randomized participants who receive at least one dose of study medication and have at least one post-baseline assessment. All statistical tests will be two-sided, with a significance level set at 0.05.

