9.2 Cognitive Outcomes

- FLAME domain scores: change from baseline
- MoCA: baseline vs Week 8
- Individual-level change plots

No adjustment for practice effects due to short follow-up.

10 Interim Analyses

No formal interim efficacy analyses are planned. Safety data will be reviewed on an ongoing basis by the medical monitor and DSMB according to protocol.

11 Changes from Protocol

Any deviations from protocol-specified analyses will be documented and justified in the Clinical Study Report (CSR).

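### The SAP's exosome model drops the protocol's log scale, baseline covariate and plate/concentration adjustment without listing the change, and specifies a redundant covariance structure

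*SAP*

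**What the plan says.** Protocol 10.3 sets the scale: "Exosome biomarker values will be natural log transformed to avoid skewness". It then specifies a linear mixed model with treatment, time, "baseline biomarker, and plate to plate variability in exosome concentration (determined by NanoSight) as fixed effects", and participant as a random effect. Protocol 10.3.4 repeats the adjustment for baseline biomarker.

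SAP 7.2 specifies a different model. Its outcome line is "Response: Change from baseline in biomarker level", and its fixed effects are treatment, categorical visit and their interaction. No section of the SAP supplied mentions a log scale, a baseline covariate, plate or exosome concentration. The dependence structure is given in two lines: "Random effects: Random intercept per participant" and "Covariance structure: Unstructured (if convergence permits, otherwise compound symmetry". If a model does not converge, its results become descriptive. Separately from the model, SAP 7.2 lists differences in mean change with 95% confidence intervals.

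SAP section 11 names no departure from the protocol. It says only: "Any deviations from protocol-specified analyses will be documented and justified in the Clinical Study Report (CSR".

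**The concern.** Two different primary models are on file, and nothing explains the move from one to the other. Three things are at stake.

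- **Scale.** The protocol's stated reason for the log is skewness. If the markers are skewed and the drug effect is multiplicative, an untransformed change score is less precise and harder to interpret than a ratio of geometric means.
- **Adjustment.** With four donepezil participants, chance differences in baseline level or exosome concentration can be large. The change score removes baseline only by subtraction, and nothing in the SAP model removes the concentration component.
- **Covariance.** A random intercept added to a full residual matrix contains a parameter that the data cannot determine. The SAP attributes possible convergence trouble to the small sample, but this redundancy is present at any sample size and its own fallback does not cure it.

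**Working it through.** **1. The plan's own figure.** Inputs: a 2.45 SD difference (Protocol 10.3), two-sided 0.05 (Protocol 10.3.1), and the statement that "a sample size of 4 participants per arm would be needed to give 80% power". For a two-sample t-test the noncentrality is d / √(1/n₁ + 1/n₂).

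- 3 per arm: 2.45/√(2/3) = 3.00, 4 df, power 61.9%.
- 4 per arm: 2.45/√(1/2) = 3.46, 6 df, power 82.1%.
- 12 vs 4: 2.45/√(1/3) = 4.24, 14 df, power 97.6%.

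The stated 4 per arm is reproduced. The calculation names no scale and no covariates, so it does not settle which model was meant.

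**2. The two models side by side.**

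| Element | Protocol 10.3 | SAP 7.2 |
|---|---|---|
| Scale | natural log | none stated |
| Baseline biomarker | covariate | subtracted only |
| Plate/exosome concentration | fixed effect | absent |
| Treatment × visit | not mentioned | included |
| Participant | random effect | random intercept |
| Further covariance structure | none stated | unstructured, else compound symmetry |

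**3. Covariance parameters.** Four post-baseline visits give a 4×4 covariance matrix with 4×5/2 = 10 distinct elements. A random intercept adds τ²J to the residual matrix, where J is the matrix of ones.

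- Unstructured plus intercept: 10 + 1 = 11 parameters, rank 10, because τ²J is already one of the unstructured matrices.
- Compound symmetry plus intercept: σ²I + cJ + τ²J = σ²I + (c + τ²)J, so 3 parameters and rank 2.
- Random intercept with independent residuals: 2 parameters, rank 2, so identified.

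In the first two cases only the split between intercept and residual is undetermined. The total covariance, and hence the treatment contrasts, can still be estimated.

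**4. Baseline covariate alone, on the ln scale.** With equal variances and correlation ρ, a change score has variance 2σ²(1−ρ) and a baseline-adjusted value σ²(1−ρ²), so the ratio adjusted/change is (1+ρ)/2. Estimating the slope with N = 16 multiplies this by 1 + 1/(16−4) = 13/12.

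- ρ = 0.4: √(0.70 × 13/12) = 0.871.
- ρ = 0.6: √(0.80 × 13/12) = 0.931.
- ρ = 0.8: √(0.90 × 13/12) = 0.987.

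The t quantile moves from 14 to 13 df and takes back a little under one percentage point. Simulated intervals are about 12%, 7% and 1% narrower. Break-even is at ρ = 24/13 − 1 = 0.85, above which the covariate gains nothing.

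**5. Scale and adjustment together.** The documents give no ln SD, no correlation and no size for the concentration component, so these are assumptions. Simulation of one post-baseline visit, 12 vs 4, lognormal marker, ρ = 0.6, effect 1.5 SD on the ln scale. Raw change is tested by a t-test; the comparator is ln follow-up adjusted for ln baseline.

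| ln SD | Raw change, decrease | Raw change, increase | ln, baseline-adjusted |
|---|---|---|---|
| 0.2 | 70% | 78% | 82% |
| 0.5 | 51% | 64% | 82-83% |
| 0.8 | 35% | 40% | 82% |

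Unadjusted ln change gives 76-77%. At ln SD 0.5, the scale therefore accounts for roughly 13 to 26 points and the baseline covariate for about 5 or 6.

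Across correlations 0.3, 0.5, 0.7 and 0.9 (ln SD 0.5, an increase), raw change gives 43%, 56%, 74% and 95%, against 68%, 76%, 90% and over 99%. Adding an exosome-concentration component of 0.5 SD, which only the protocol's model adjusts for and which is assumed to be measured without error, gives 30%, 37%, 47% and 62% against 64%, 70%, 81% and 96%. Where there is no treatment effect, rejection stays near 5% for every method.

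**The case against.** The strongest reply is that this is an exploratory 16-person study. SAP 2.3.1 says it is not powered for confirmatory testing, and the SAP plans estimation rather than a test at a fixed level, so power is not its criterion. That stands, although the protocol still says "All statistical tests will be two-sided, with a significance level set at 0.05" and gives a power calculation. Power serves here as a measure of precision, and scale and adjustment decide the estimates and intervals on which the SAP says it will rely.

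Other parts of the reply also stand. Change from baseline agrees with the endpoint in Protocol 10.3.3, so the conflict is over scale and adjustment. The random intercept is not new, since the protocol already treats participant as random. SAP 4.5 gives the primary outcome a baseline-to-Week-8 timeframe, so the time point is indicated even though SAP 7.2 names no contrast. The redundancy depends on reading the covariance line as the residual matrix. Analysis on the raw scale is inferred from the SAP's silence, though it is the natural reading. The size of the loss depends on assumed values, and at low skewness it is modest.

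A reader might infer three stronger things that the documents do not support:

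- **That the between-arm estimate would be lost.** The mean change differences with confidence intervals are listed separately and survive a model failure. Whether a redundant model fails to converge depends on the software.
- **That the model was chosen with results in view.** SAP 1.1 says the SAP is final before database lock and biomarker unblinding. Only the justification for departing from the protocol is left until later.
- **That the intervals will be too short.** The SAP names no degrees-of-freedom method, but it does not specify normal-theory intervals either.

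**Conclusion.** The concern holds as an unexplained mismatch on the primary endpoint together with a redundant covariance specification. The mismatch is plain from the text: three elements of the protocol's model are missing from SAP 7.2 and section 11 does not say so. The redundancy is exact under the residual-matrix reading, for both the first choice and the fallback. Its consequence is a possible singular or non-converging fit, and then reliance on unadjusted mean change differences.

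The loss of precision cannot be fixed from the documents. Under the assumptions above (ρ = 0.6, 1.5 SD) it is about 18 to 32 power points at ln SD 0.5, more at ln SD 0.8, and 4 to 12 points at ln SD 0.2. At the moderate and high ln SDs most of it comes from the scale. The baseline covariate alone is worth about 12% of interval width at correlation 0.4 and almost nothing at 0.8. The 1.5 SD effect is smaller than the protocol's 2.45 SD. At 2.45 SD, ρ = 0.5 and the ln scale, unadjusted change and baseline adjustment give 97.6% and 99.1%, so the covariate hardly matters there. The simulations show no inflation of false positives.

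**What to change.** In SAP 7.2, specify:

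- Response: ln(biomarker) at Weeks 2, 4, 6 and 8.
- Fixed effects: treatment, visit, treatment × visit, ln baseline biomarker, and the exosome-concentration/plate adjustment of Protocol 10.3.
- One covariance specification only: an unstructured residual matrix without a random intercept, falling back to compound symmetry. A random intercept with independent residuals is the equivalent form of that fallback when the within-participant covariance is not negative.
- Estimation by REML with a small-sample degrees-of-freedom method, such as Kenward-Roger.
- Main contrast: Week 8, reported as a ratio of geometric means with its 95% confidence interval.

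In SAP section 11, list and justify any remaining departure from Protocol 10.3 before biomarker results are unblinded.

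The cost is SAP wording and a few degrees of freedom. It is higher if plate enters as a factor with several levels, since each extra plate uses one. The number of plates is not given and panel details sit in SOPs that were not supplied, so the SAP should say whether the adjustment is a continuous concentration term, a plate factor or both.

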8.1 Safety and Tolerability

Summarized by treatment arm:

- Incidence of AEs and SAEs
- GI AEs of special interest
- Laboratory abnormalities

- ECG changes
- Dose reductions and discontinuations

AEs will be coded using MedDRA.

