In this open-label Phase 1b study, eligible participants with early or mild Alzheimer's disease (AD) will be randomized 6:2 to receive phenserine or donepezil for a total treatment duration of 8 weeks. Participants will dose escalate at 2- to 4-week intervals (depending on their treatment assignment) to achieve a maintenance dose level that is well tolerated. The objectives of the study are to characterize phenserine's pharmacodynamic activity in comparison to donepezil as evaluated by changes in exosome biomarkers and effects on cognition. In addition, safety, tolerability and pharmacokinetic assessments will be evaluated. The data from the study will be used to select an appropriate dose range for a subsequent Phase 2 proof-of-concept study to characterize phenserine's efficacy and safety in people with early or mild Alzheimer's Disease (AD) over a longer treatment duration.

The protocol is further summarized in the following synopsis and in the study schema that is presented in Figure 1. In addition, a detailed Schedule of Activities is presented in Table 1.

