To evaluate compliance, the study will measure the extent to which participants take the study medication according to the protocol. Compliance will be assessed using the subject diary and the registration of returned capsules.

Exploratory Objectives:

To evaluate changes in specific biomarkers of Alzheimer's Disease (AD) in cerebrospinal fluid (CSF): A β 1-40, A β 1-42, Tau, and p-tau, and in blood plasma: p-tau217 and NfL.

To assess phenserine's potential short-term effects on specific cognitive tests using the FLAME Memory Composite and other cognitive sub-tests.

To evaluate changes in overall cognitive function using the Montreal Cognitive Assessment (MoCA):

Primary Endpoint:

Changes in exosome biomarkers of pre-programmed cell death, synaptic integrity and function, neuroinflammation, and AD-related protein trafficking in participants treated with phenserine versus those treated with donepezil. Although patients and site staff will be unblinded to the treatment modality administered, they will be blinded to the results of the biomarker evaluations until the study is completed.

Key Secondary Endpoints:

Safety and tolerability of phenserine compared to donepezil in participants with early or mild AD based on the frequencies of reported or observed adverse events (AEs) and serious adverse events (SAE), vital signs, clinical laboratory evaluations, ECGs, and modified CSSRS scores.

Other Secondary Endpoints:

Pharmacokinetic parameters will be assessed at steady state for determination of dose-response relationships for phenserine and donepezil.

Evaluate the proportion of participants in the phenserine arm who achieve the target AChE inhibition of approximately 45%, stratified by dose regime and assess the time required to reach the target AChE inhibition of ~45% and the duration participants maintain this inhibition during the treatment period. Blood samples will be analyzed for Acetylcholinesterase (AChE) activity using a modified Micro-Ellman method (22) normalized to recombinant AChE enzyme activity (refer to Appendix 10).

Compliance will be recorded, based on drug count and subject diary, including the proportion of participants complying with the treatment schedule. Compliance is defined as drug intake within 80-120% of the scheduled dosing.

Exploratory Endpoints:

Assess changes in Alzheimer's Disease (AD) biomarkers in cerebrospinal fluid (CSF): A β 1-40, A β 1-42, Tau, and p-tau, and in blood plasma: p-tau217 and NfL.

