3.1. Table 2. Objectives and endpoints

Objectives	Endpoints
Primary	
To assess the effects of phenserine compared to donepezil on exosome biomarkers of cell death in people with early or mild AD.	Changes in endosomal biomarkers of pre-programmed cell death, synaptic integrity and function, neuroinflammation, and AD-related protein trafficking in participants treated with phenserine versus those treated with donepezil. Although patients and site staff will be unblinded to the treatment modality administered, they will be blinded to the results of the biomarker evaluations until the study is completed.
Secondary	
To evaluate the safety and tolerability profile of phenserine at ascending doses up to 10 mg tds as compared to donepezil at doses up to 10 mg od in participants with early or mild AD.	Safety and tolerability of phenserine compared to donepezil in participants with early or mild AD based on the frequencies of reported or observed adverse events (AEs) and serious adverse events (SAE), vital signs, clinical laboratory evaluations, ECGs, modified CSSRS scores.
Other secondary	
To evaluate steady state blood levels of phenserine and donepezil for the purpose of characterizing and comparing dose-response relationships for pharmacodynamic outcomes and key safety assessments.	Pharmacokinetic parameters will be assessed at steady state for determination of dose-response relationships for phenserine and donepezil
To evaluate the proportion of participants in the phenserine arm who achieve the target cholinesterase inhibition of approximately 45% across different dosing regimens, as well as the time required to reach the target and the duration of maintaining this inhibition.	Proportion of participants in the phenserine arm achieving the target cholinesterase inhibition of ~45%, stratified by dosing regimen and the time to reach the target inhibition and the duration of maintaining this target will be assessed and recorded
To evaluate compliance, the study will measure the extent to which participants	Compliance will be recorded, based on drug count and subject diary, including the proportion of

take the study medication according to the protocol. Compliance will be assessed using the subject diary and the registration of returned capsules.	participants complying with the treatment schedule. Compliance is defined as drug intake within 80-120% of the scheduled dosing.
Exploratory	

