2.3 Exploratory Objectives

- Changes in CSF and plasma AD biomarkers
- Short-term cognitive effects using FLAME and MoCA

Endpoints are defined exactly as per Protocol Section 3 and Table 2

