8.3 AChE Inhibition

- Proportion achieving $\geq 45\%$ inhibition
- Time to reach target inhibition
- Duration above target threshold

Summarized descriptively and graphically.

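### SAP 8.1 omits the dose-level safety summary that Protocol 10.3 specifies, and SAP 8.3 does not carry out the dose stratification of AChE attainment

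*SAP*

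**What the plan says.** **Safety.** Protocol 10.3 lists AEs, TEAEs, SAEs, important laboratory findings and AE-related discontinuations, and says that they "will be summarized for each treatment arm and dose level". SAP 8.1 lists AEs and SAEs, gastrointestinal AEs, laboratory abnormalities, ECG changes, and dose reductions and discontinuations, all under the instruction "Summarized by treatment arm". Dose level is not mentioned.

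**AChE inhibition.** Protocol Section 3 defines a secondary endpoint on the proportion of phenserine participants "who achieve the target AChE inhibition of approximately 45%, stratified by dose regime". Protocol Table 2 repeats this: "stratified by dosing regimen and the time to reach the target inhibition". SAP 2.3 adopts these definitions: "Endpoints are defined exactly as per Protocol Section 3 and Table 2". SAP 8.3 then lists the proportion reaching target, the time to reach it and the time above it, "Summarized descriptively and graphically", without dose strata. The outcome table in SAP 4.5 has none either.

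**Purpose.** Protocol Section 1 states: "The data from the study will be used to select an appropriate dose range for a subsequent Phase 2 proof-of-concept study". Protocol Section 3 also lists, as a secondary objective, dose-response for pharmacodynamic outcomes and for key safety assessments.

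**The concern.** Each phenserine participant is planned to pass through three dose levels in eight weeks. An arm-level incidence counts a participant once, whichever level the event arose at. A study report that followed SAP 8.1 literally would give adverse-event, laboratory and discontinuation figures for phenserine as a whole. It would have no planned table showing at which dose they occurred, and that is the information a Phase 2 dose choice needs from the safety data.

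For AChE, an overall proportion reaching 45% at some time during treatment does not say which regimen achieved it. The stratification is part of the endpoint, but the analysis section does not say how it will be done or how a sample is attributed to a regimen.

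**Working it through.** The plan states no figure for this point, so there is nothing to reproduce. The check compares the texts, with some arithmetic on exposure.

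**1. Is dose level restored elsewhere in the SAP?**

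| Place | What it offers | By-dose safety? |
|---|---|---|
| SAP 2.3 | Imports endpoints from Protocol Section 3 and Table 2 | No: the by-dose safety rule is in Protocol 10.3 |
| SAP 7.1 | Exosome biomarkers by visit | No |
| SAP 8.1 | Safety by arm, including a count of dose reductions | No |
| SAP 8.2 | Exposure-response plots against AChE inhibition and exosome markers | No: safety is not plotted |
| SAP 8.3 | AChE proportion, time and duration | Not safety; no dose strata |
| SAP 11 | Leaves departures from the protocol to the study report | No change listed |

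The safety breakdown is therefore neither implemented nor declared as changed. The AChE stratification survives in the endpoint definition but not in the analysis text.

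**2. What does an arm-level table pool?** Inputs are 12 phenserine and 4 donepezil participants (SAP 3) and the planned steps in Protocol Tables 3 and 4. The assumption is that everyone titrates on schedule and completes.

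- 5 mg bd = 10 mg/day, Weeks 1–2: 12 × 14 = 168 participant-days
- 10 mg bd = 20 mg/day, Weeks 3–4: 12 × 14 = 168 participant-days
- 10 mg tds = 30 mg/day, Weeks 5–8: 12 × 28 = 336 participant-days
- Phenserine total: 168 + 168 + 336 = 672 participant-days (96 person-weeks)
- Donepezil: 4 × 28 = 112 participant-days at 5 mg od and 4 × 28 = 112 at 10 mg od

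On the same assumption, the AChE samples at Weeks 2, 4, 6 and 8 give 12 at 5 mg bd, 12 at 10 mg bd and 12 × 2 = 24 at 10 mg tds.

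**3. What is lost? An illustration with assumed counts.** Suppose 3 of 12 phenserine participants have a given event. The arm-level figure is 3/12 = 25% (exact Clopper-Pearson 95% CI 5.5% to 57.2%). It is the same if all three events began at 5 mg bd or all three at 10 mg tds. In the second case a by-dose table would show 0/12 at each lower level (exact upper 95% limit 26.5%) and 3/12 at the top. The arm-level table cannot tell these cases apart.

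**4. Can visit stand in for dose?** Only roughly. Protocol 6.6 makes each step depend on tolerability and returns participants who cannot tolerate a step to the previous level. A Week 6 or Week 8 record may therefore belong to different regimens in different people. SAP 8.1 does not tabulate safety by visit in any case.

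**The case against.** Several points on the other side are fair.

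- **The protocol also describes arm-level safety.** Protocol 10.3.5 and 10.3.7 plan comparisons of AE frequency between the two groups and do not mention dose, and SAP 8.1 agrees with them. This stands as a fact, but those sections do not withdraw the rule in 10.3. A between-arm comparison and a dose-level tabulation can coexist, and the SAP keeps only one.
- **A reader might infer that the trial would report nothing by dose.** The documents do not support that. Exposure-response plots, by-visit exosome summaries and a count of dose reductions remain. The planned steps are also tied to weeks, so time to AChE target carries some dose information. None of these is a by-dose safety output.
- **A reader might infer that the AChE stratification has been abandoned.** It has not, because SAP 2.3 imports it. The gap is that SAP 8.3 does not carry it out.
- **A reader might size the problem from the nausea rates in Protocol 2.3.1, 9% at 10 mg bd and 19% at 15 mg bd.** Those come from an earlier trial, and 15 mg bd is not a regimen here. The protocol itself argues that dividing the daily dose lowers peak concentration and so side effects. The rates do not measure what is lost in this trial.
- **Cells will be very small.** This is true. It argues for showing counts with exposure and avoiding inference. It does not argue for pooling, since the SAP is descriptive throughout.
- **No table can separate dose from time on drug, or from the selection of people who tolerated earlier steps.** This is also true. The donepezil arm does not solve it: it has four participants and its own dose increase is planned from Week 5, the same point as the step to 10 mg tds.

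**Conclusion.** The concern holds in two parts. First, SAP 8.1 leaves out a safety breakdown that Protocol 10.3 specifies, SAP 11 does not declare the omission, and no SAP output relates safety to dose. Second, SAP 8.3 does not specify the dose-regimen stratification contained in its own imported endpoint.

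On planned exposure, one arm-level figure covers three daily doses over 168, 168 and 336 participant-days. This assumes full titration and completion; step-downs and dropouts would reduce exposure at the top step. The 3-of-12 example uses assumed counts and shows only that the arm-level figure carries no information about dose.

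The primary exosome analysis is not affected. The gap limits how well the report can serve its dose-range purpose and the dose-response objective for safety. It should be closed while the SAP can still be amended, that is, before database lock.

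**What to change.** Amend the SAP as follows.

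1. **SAP 8.1.** Keep the arm-level summary and add one by actual dose level at onset, in both arms. For each level give participants exposed, participant-days, and the number of participants with at least one AE, SAE, gastrointestinal AE, laboratory abnormality, dose reduction or discontinuation.
2. **SAP 8.3.** Report percent AChE inhibition and attainment of the 45% target by actual dose regimen at sampling.
3. **Assignment rule.** State how an event or sample is given to a dose level. The rule should cover events on the day of a dose change, events after a step-down or after the last dose, and samples taken at a visit where a new dose is dispensed.
4. **Footnote.** Say that in a tolerability-guided titration, dose is confounded with time on drug and with tolerance of the earlier steps, so differences between dose rows are not dose effects.
5. **Alternative.** If the sponsor prefers arm-level safety only, list and justify that change in SAP 11 and reconcile it with Protocol 10.3.

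The tables should stay descriptive, as counts with exposure. Event-rate intervals that treat repeat events in one person as independent would mislead with 12 participants.

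The cost is a few extra tables from dosing, AE and AChE data already collected, plus the programming of a dose-at-onset variable. The drawback is very small cells.
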